#### 4.9 Enrollment Criteria

##### 4.9.1 Inclusion Criteria

- 1) Subject must be  $\geq 18$  and  $\leq 95$  years of age
- 2) Clinical diagnosis of chronic limb-threatening ischemia, defined as any of the following clinical assessments: previous angiogram or hemodynamic evidence of severely diminished arterial inflow of the index limb (e.g.,  $\text{ABI} \leq 0.39$ ,  $\text{TP} / \text{TcPO}_2 < 30$  mm Hg) and
  - a) Rutherford Classification 5, ischemic ulceration *or*
  - b) Rutherford Classification 6, ischemic gangrene
- 3) Subject has been assessed by the Principal Investigator, reviewed by the Independent Review Committee (IRC), and determined that no conventional distal bypass surgical or endovascular therapy for limb salvage is feasible due to either a) absence of a usable pedal artery target (endovascular or surgical approach), or b) the presence of a pedal artery target with absence of a viable single-segment vein in either lower extremity or either arm that could be used for autogenous vein conduit.
- 4) Proximally, the Target In-flow Artery at the cross-over point must fall within the recommended vessel diameter ranges for the LimFlow stent graft by visual estimation.
- 5) Prior stent(s) to the infrainguinal arteries (e.g., iliac, SFA, and popliteal) are allowed.

- 6) Planned minor amputation (e.g., partial toe, ray or proximal foot/transmetatarsal) of target extremity within 30 days after the index procedure is allowed.
- 7) Subject is willing and able to sign the informed consent form.
- 8) Subject is enrolled in an acceptable wound care network and has an adequate support network to ensure that subject is compliant with medication regimen and follow-up study visits.
- 9) Prior to enrollment (7-day window), women of childbearing potential must have a negative pregnancy test.
- 10) Primary wound is stable (e.g., not rapidly deteriorating and/or showing signs of healing)
- 11) Stable glycemic control, HbA1C < 10% (<269mg/dL)
- 12) Subjects requiring dialysis may be included, provided they meet *all* the following requirements:
  - On dialysis for  $\geq 6$  months
  - Autologous arteriovenous (AV) fistula or peritoneal access used for hemodialysis
  - Serum albumin  $\geq 30$  g/liter
  - BMI  $\geq 20$

#### 4.9.2 Exclusion Criteria

- 1) Subjects will be excluded from participating in this study if they meet any of the following criteria prior to initiation of the endovascular procedure: Concomitant hepatic insufficiency, thrombophlebitis in the target limb, or non-treatable coagulation disorder within the past 90 days.
- 2) Active immunodeficiency disorder or currently receiving immunosuppressant therapy for an immunodeficiency disorder.
- 3) Prior peripheral arterial bypass procedure above or below the knee which would inhibit proximal inflow to the stent graft or interventional revascularization procedure within 30 days.
- 4) Previous major amputation of the target limb, presence of a wound requiring a free flap, or absence of adequate viable tissue.
- 5) Life expectancy less than 12 months.
- 6) Documented myocardial infarction or stroke within previous 90 days.
- 7) Active infection (e.g., fever, significantly elevated WBC count  $>20.0 \times 10^9/L$ , and/or positive blood culture) at the time of the index procedure that may preclude insertion of a prosthesis or require major amputation (e.g., osteomyelitis proximal to metatarsals).
- 8) Known or suspected allergies or contraindications to aspirin or P2Y12 inhibitors, heparin, stainless steel, nitinol or contrast agent that cannot be adequately pre-treated.
- 9) Subject is currently taking anti-coagulants, which in the opinion of the investigator, interferes with the subject's ability to participate in the study (i.e., intermittent interruption of therapy for procedure may compromise subject's safety).
- 10) Lower extremity vascular disease that may inhibit the procedure and/or jeopardize wound healing (e.g., vasculitis, Buerger's disease, significant edema in the target limb, deep venous thrombus in the target vein, hyperpigmentation, or medial ulceration above the ankle).
- 11) Significant acute or chronic kidney disease with a serum creatinine of  $> 2.5$  mg/dl in subjects not undergoing dialysis.
- 12) Severe heart failure (e.g., NYHA Class IV), which in the opinion of the investigator may compromise subject's ability to safely undergo a percutaneous procedure.

- 13) Any significant concurrent medical, psychological, or social condition, which may significantly interfere with the subject's optimal participation in the study in the opinion of the investigator.
- 14) The subject is currently participating in another investigational drug or device study that has not completed the primary endpoint or that clinically interferes with the endpoints of this study.
- 15) Subject is unwilling, unable, or unlikely for cognitive or social reasons to comply with any of the protocol or follow-up requirements.

##### 4.10.2 Independent Review Committee (IRC)

The IRC will review potential study candidates to evaluate their eligibility for the study, specifically to determine that no conventional distal bypass surgical or endovascular therapy for limb salvage is feasible due to the absence of a suitable distal target artery. The IRC will operate according to an IRC Charter, which will detail the scope and purpose of the committee.

##### 4.10.3 Core Laboratory

An independent core laboratory will be utilized in this clinical study for the reporting of technical success and wound-related clinical data. Wound data (e.g., images and measurements) collected by the sites will be compiled, reviewed, and analyzed for healing of target and all wounds (progression, completion, confirmation) by the core laboratory. A Core Lab Manual of Operations and Procedures will be maintained by the core lab.

##### 4.10.4 Data Monitoring Committee (DMC)

The DMC will act in an advisory capacity to the Sponsor to monitor participant safety and evaluate the progress of the study and will alert Sponsor to possible concerns related to the conduct of the Study, as appropriate. DMC members will consist of at least three independent medical professionals who are not PROMISE Trial Investigators and without any conflict of interest. The committee members may include experts in the fields of interventional cardiology, vascular surgery, interventional radiology, and biostatistics. The DMC will operate according to a DMC Charter, which will detail the scope and purpose of the committee.

##### 4.10.5 Clinical Events Committee (CEC)

The CEC will assess important endpoints of a trial and determine whether each meet protocol-specified criteria. CEC members will be independent medical professionals qualified by training and experience, with expertise in the fields of interventional cardiology, vascular surgery, and interventional radiology without conflict of interest. The CEC will operate according to a CEC Charter, which will detail the scope and purpose of the committee. A medical monitor (MM) will be responsible for training the CEC members on the protocol, the CEC Charter, and on the standard definitions and Protocol/Charter defined terms used for event adjudication. The MM will review each adverse event to determine whether it meets the criteria for adjudication.

**4.11 Data Management**

Electronic Case Report Forms (eCRF) will be collected in an electronic database (EDC) used to capture data for the safety and effectiveness analysis. Sites will be required to maintain source documentation, in accordance with GCP guidelines, 21 CFR 812, and ISO 14155 to substantiate all data collected. Primary data collection based on source-documented chart reviews will be performed by the clinical research team. The Sponsor will provide adequate source document worksheets for capture of study-specific data during the procedure and follow-up visits that may not normally be collected during routine procedures or visits.

[figure not shown]
**4.12 Monitoring**

The clinical site will be monitored periodically by the Sponsor’s personnel, or Sponsor’s designee, for protocol adherence, accuracy of eCRFs, and compliance to applicable regulations. Any observations of non-compliance will be reviewed with the Principal Investigator. Any evident pattern of ongoing non-compliance may result in corrective actions by the Sponsor, including potential study suspension, as deemed appropriate by the Sponsor. The Sponsor will review significant new information, including unanticipated adverse device events and ensure that such information is provided to the appropriate regulatory agencies, the investigators and to all reviewing investigational review boards (IRBs) or Ethics Committees (ECs) as required by applicable regulations.

**4.13 Training**

The implanting physician(s) will receive training prior to their first case. A didactic presentation will cover the following areas: device components, procedure setup, implant procedure, post procedure requirements, protocol and regulatory requirements, screening procedures, and the Independent Review Committee approval process. The primary investigators and research coordinators will attend the didactic training session. All primary investigators will be required to attend the detailed bench model training and session. Research coordinators and ancillary staff will be encouraged to attend.

A LimFlow System implant procedure may be performed following the formal training.

A LimFlow proctor will attend all implant procedures.

**4.14 Subject Recruitment**

Subjects who have a clinical diagnosis of chronic limb-threatening ischemia and have been determined by their physician to have no surgical or endovascular treatment possible (i.e., “no option”) will be recruited.

**4.15 Subject Compensation**

Subjects may be compensated for expenses associated with attending study sessions (e.g., travel costs) in

this study.

## 5. Study Procedures and Evaluations

### 5.1 Screening and Enrollment

#### 5.1.1 Preliminary Screening

Prior to obtaining written informed consent, the subject's existing medical records may be reviewed to determine whether or not the subject might be an acceptable candidate for this study. If initial review of the medical records indicate that the subject may be eligible, the informed consent process may commence.

#### 5.1.2 Informed Consent

The Investigator or a designated member of his/her staff should approach the subject to obtain written informed consent. As much as possible, non-technical language shall be used that is understandable to the subject. If the family of the subject is available, they should also be consulted. The background of the proposed study and the benefits and risks of the procedures and study should be explained. The subject will be given the plain language study specific Informed Consent Form (ICF) which describes all information that is relevant to study participation. The subject should be provided with ample time to read the consent form and discuss it with their family and physician. The subject must sign the consent form prior to enrollment or upload of any protected health information to IRC for screening. This form or a modification of it must have prior approval of the study site's Institutional Review Board (IRB) or Ethics Committee (EC). Subjects may not be consented after receiving any medication that might alter their ability to comprehend the consent form (*e.g.*, sedatives, narcotics, etc.).

The subject and the authorized study personnel obtaining informed consent must sign and date the ICF. A copy must be given to the subject. It is not expected that enrollment into this study will be under emergency circumstances; therefore, emergency consenting procedures do not apply. **Written informed consent must be obtained prior to performing any *protocol driven* tests or procedures that are not standard of care.** Once written consent has been obtained, the subject will be entered on a screening log which will be maintained at each site. All subjects *who provide written informed consent* will be entered on the screening log regardless of whether or not they continue on to enrollment in the study. Subjects who provide written informed consent and remain interested in study participation will begin the screening process. As appropriate, important and new information will be provided to new and existing subjects throughout the duration of the study.

If a subject is unable to make the decision to participate (*e.g.*, mentally ill, demented or otherwise cognitively handicapped person), the subject will be excluded.

Table 1: Study Assessment Schedule

	Visit 1	Visit 2	Visit 3	Visit 4	Visit 5	Visit 6	Visit 7	Visit 8	Visit 9	Visit 10	Visit 11
	Baseline and Screening (-6M to proc)	Treatment (Day 0) to Discharge	2 Weeks (+/- 3 Days)	1 Month (+/- 1 week)	2 Month (+/- 2 weeks)	3 Month (+/- 2 weeks)	6 Month (+/- 2 weeks)	9 Month (+/- 2 weeks)	1 Year (+/- 4 weeks)	2 Year (+/- 4 weeks)	3 Year (+/- 4 weeks)
Written Informed Consent	√										
Baseline imaging  that establishes pedal artery target	√										
Inclusion / Exclusion criteria, including IRC, assessment that subject is not a candidate for conventional surgical or endovascular limb salvage procedures	√										
Demographic data, medical history, medication review, physical exam, and pregnancy test (if applicable)	√										
Additional exams if required to confirm eligibility 	√										
Pedal vein assessment for case planning	√										
Review of medications / dual anti-platelet regimen 	√	√	√	√		√	√	√	√	√	√
Rutherford Classification (RCC)	√			√		√	√	√	√	√	√
WIFI Classification (ischemia measured via TcPO 2  or Toe Pressure)	√		√	√		√	√	√	√	√	√
Wound healing assessment, and photographs 	√		√	√		√	√	√	√	√	√
Wound culture, if suspected infection 	√	√	√	√		√	√	√	√	√	√
Pulse evaluation via hand-held continuous wave Doppler distal to the stent graft 		√ 	√	√		√	√	√	√	√	√
Serum Creatinine	√			√			√				
Numeric Pain Scale Rating (1-10)	√			√		√	√	√	√	√	√
Procedural angiogram  and device performance data		√									
Procedure time, defined from sheath insertion to final catheter removal		√									
Fluoroscopy and Contrast for the index procedure		√									
Device- or procedure-related AE and SAEs 		√	√	√	√	√	√	√	√	√	√
Assessment of amputation and/or re-intervention of the Stent Graft			√	√		√	√	√	√	√	√
Duplex Ultrasound Exam to assess Stent Graft patency 				√	√	√	√	√	√	√	√
All-cause mortality		√	√	√	√	√	√	√	√	√	√

 E.g., an angiogram without procedure or angiogram from a failed recanalization  
 Including an MRI, if there is suspected osteomyelitis and bypass conduit vein mapping if there is a pedal artery target and the ipsilateral saphenous vein has not been previously harvested  
 Dual antiplatelet therapy is recommended for 3 months post-procedure. At a minimum, all subjects are recommended to be started on DAPT at least one week before procedure or adequately pre-loaded with DAPT as per institution practice.  
 TcPO2 will be measured at 2 constant points on the dorsum of the midfoot through the 12-month follow-up at sites who perform TcPO2.  
 Prior to any re-intervention of the stent graft, an angiogram/image and wound photograph should be obtained for adjudication purposes.  
 Optional; Sponsor will reimburse for culture any time there is a suspected infection.  
 Hand-held continuous wave Doppler will be performed immediately post-procedure and again between 4 and 30 hours post-procedure to assess for acute thrombosis; any findings of acute thrombosis in this time frame must be reported to the Sponsor within 24 hours of the exam.  
 Must include pre- and post-index arteriogram showing vasculature from hip to foot  
 Review of any hospitalizations or procedures involving the index limb, and/or potentially related to the device or procedure; all SAEs through 6 months. For subjects out of area or who refuse to come in for a visit, a telephone assessment should be conducted to capture as much information as possible at the time point.  
 If any LimFlow device is introduced but stent-graft implantation is either not attempted or unsuccessful, subjects will be followed for safety for 30 days with a minimum of phone calls to assess AFS.  
 May be performed at any additional non-study visit as standard of care, as indicated by clinical symptoms.

### 5.2 Baseline and Screening (within 6 months prior to index)

Baseline evaluation will be performed after the subject has provided written informed consent in order to ensure that the subject is an appropriate candidate for this study and to obtain baseline values for study endpoint evaluation. If the subject continues to meet the study's enrollment criteria and continues to be willing and able to participate in the study protocol, the subject undergoes baseline evaluation and continued assessment for eligibility.

Baseline visit and data collection can occur anytime within six months before the LimFlow procedure up to the time of procedure (unless otherwise indicated). Subjects not eligible per the angiographic requirements (determined at the time of the screening) will be screen-failed from the study and the reason for exiting documented in the screening and enrollment logs.

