**Secondary Endpoints**

**Primary Patency:** Defined as absence of occlusion of the endovascular intervention that is maintained without the need for additional or secondary surgical or endovascular procedures, at 30 days and 6 months.

**Primary Assisted Patency:** Defined as absence of occlusion of the endovascular intervention maintained with the use of additional or secondary surgical or endovascular procedures, as long as occlusion of the primary treated site has not occurred, at 30 days and 6 months.

**Secondary Patency:** Defined as absence of occlusion of the endovascular intervention that is maintained with the use of additional or secondary surgical or endovascular procedures after occlusion occurs, at 30 days and 6 months.

**Limb Salvage:** Defined as percentage of subjects with freedom

from above-ankle amputation of the index limb, evaluated at 30 days, 3 and 6 months.

**Change in Rutherford Classification:** Defined as a change of one class or greater, as evaluated at 30 days, 3 and 6 months.

**Technical Success:** Defined as the successful creation of an arteriovenous fistula in the desired limb location with immediate morphological success.

**Procedural Success:** Defined as the combination of technical success, and absence of all-cause death, above-ankle amputation or clinically driven major re-intervention of the stent graft at 30 days.

**Target Wound Healing:** Defined as complete healing of the patient's target wound as evaluated at 30 days, 3, 6, 9 months, and 1 year.

**All Wound Healing:** Defined as complete healing of the patient's wounds as evaluated at 30 days, 3, 6, 9 months, and 1 year.

**All Wound Area Reduction:** Defined as reduction in area of the patient's wounds as evaluated at 30 days, 3, 6, 9 months, and 1 year.

**Freedom from Contrast-Induced Nephropathy:** Defined as subjects without acute (within 72 hours after intravenous contrast administration) impairment of renal function, measured as an absolute  $\geq 0.5$  mg/dL (44  $\mu\text{mol/L}$ ) increase compared to baseline SCr value that results in a value above the upper limit of the normal range.

**Procedure Time:** Defined as the time of the first puncture (venous or arterial) to when the last catheter is removed.

**Radiation Exposure:** Defined as patient radiation exposure (in milligray) during the procedure.

**Contrast Volume:** Defined as the total volume of contrast media (in milliliters) given during the procedure.

---

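### The baseline for wound area and Rutherford class may be up to 6 months old at the procedure with no Day 0 repeat, so two descriptive secondary endpoints can mix pre-procedure with post-procedure change

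*Protocol*

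**What the plan says.** - **Purpose of the visit.** Protocol 5.2 says the baseline evaluation serves in part "to obtain baseline values for study endpoint evaluation". It is the endpoint baseline, not only an eligibility screen.
- **Window.** The same section reads "Baseline visit and data collection can occur anytime within six months before the LimFlow procedure up to the time of procedure", and adds a proviso that leaves room for exceptions. The only dated exception found is the 7-day window for the pregnancy test (inclusion criterion 9).
- **Schedule.** Table 1 heads the Visit 1 column "Baseline and Screening (-6M to proc". The rows "Rutherford Classification (RCC" and "Wound healing assessment, and photographs" are ticked there and blank under Treatment (Day 0) to Discharge. The next ticks are at 2 weeks for wounds and 1 month for Rutherford class.
- **Procedure day.** The intra-operative data list in Protocol 5.6 contains neither measure. Protocol 5.8 places wound imaging at screening and at follow-up.
- **Endpoints.** All Wound Area Reduction is "Defined as reduction in area of the patient" and continues with that patient's wounds at 30 days, 3, 6 and 9 months and 1 year. Change in Rutherford Classification is a shift of at least one class at 30 days, 3 and 6 months. Neither definition names the reference value.
- **SAP.** It defines no analysis baseline and no maximum age for one. Section 7 makes the secondary endpoints descriptive, with 95% confidence intervals and no tests. Section 9.6 offers wound area and Rutherford class as candidate variables in exploratory Cox models.

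**The concern.** A change-from-baseline endpoint describes what followed the procedure only if the baseline describes the limb at the procedure. Here the written rule permits a baseline taken months earlier and asks for no new measurement on the day. Whatever happens to the wound or the class in between is counted in the endpoint as if it had followed the device.

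In a two-arm trial such drift would tend to appear in both arms. This trial has one arm, so nothing in the design separates it from the treatment result. What is at stake is how the reported wound-area reduction and Rutherford change can be read. A confidence interval around either figure does not reveal that the reference value was out of date.

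**Working it through.** The plan states no figure on this point to reproduce. The check is the arithmetic of the window, followed by illustrations with assumed values.

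**Inputs.** The baseline falls 0 to 6 months before the procedure (Protocol 5.2, Table 1). A month is 30 days (Protocol 5.8), so the window is 6 × 30 = 180 days. Visit windows are ±7 days at 30 days and ±14 days at 3 and 6 months (Table 1, counting a week as 7 days).

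**Gap from baseline to assessment.** The shortest gap has the baseline on Day 0 and an early visit: visit day − visit window. The longest has a 180-day-old baseline and a late visit: 180 + visit day + visit window.

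| Assessment | Shortest gap | Longest gap |
|---|---|---|
| 30 days | 30 − 7 = 23 days | 180 + 30 + 7 = 217 days |
| 3 months | 90 − 14 = 76 days | 180 + 90 + 14 = 284 days |
| 6 months | 180 − 14 = 166 days | 180 + 180 + 14 = 374 days |

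Two subjects can both contribute to the 30-day estimate with observation periods of 23 and 217 days.

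**Wound area, assumed values.** Let r be the true reduction from Day 0 to the visit and g the relative change in area between baseline and Day 0. The endpoint then shows 1 − (1 + g)(1 − r). With r = 30%:

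| g (assumed) | Apparent reduction |
|---|---|
| −30% | 1 − 0.70 × 0.70 = 51% |
| 0 | 1 − 1.00 × 0.70 = 30% |
| +25% | 1 − 1.25 × 0.70 = 12.5% |
| +50% | 1 − 1.50 × 0.70 = −5% |
| +100% | 1 − 2.00 × 0.70 = −40% |

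The error runs in either direction. The documents give no value for g, so the table shows the mechanism and is not an estimate.

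**Rutherford class.** Entry is limited to classes 5 and 6, and the endpoint threshold is one class. A single step before the procedure therefore equals the whole threshold. A subject who is class 5 at screening, 6 on Day 0 and 6 at 30 days is recorded as changed, although nothing changed after the procedure. One who goes from 5 to 6 and back to 5 is recorded as unchanged, although the class improved after the procedure.

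**Where it does not reach.** Target Wound Healing and All Wound Healing are defined by complete healing and need no baseline area. Amputation-free survival at 180 days counts events after Day 0 and uses no baseline measurement.

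**The case against.** **The window is a ceiling.** A baseline on the day of the procedure is allowed, the visit must follow consent, and the documents do not report actual lags. This stands: old baselines may be rare. A reader might infer that most baselines are months old, but nothing in either document shows that. The point is that the rule permits it and no analysis would detect it.

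**Eligibility limits drift.** The primary wound must be stable, and the exclusions apply up to the start of the procedure. This stands in part. These criteria limit gross change, but they set no date and require no new measurement.

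**The consequences are small.** SAP Section 7 is descriptive. All Wound Area Reduction appears in the SAP synopsis but not in the Section 3.2 list to which Section 7 refers. Both facts are correct and keep the point minor. Protocol 4.8 still lists the endpoint.

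**Other documents may cover it.** Wound data go to a core laboratory with its own manual (Protocol 4.10.3), which is not among the documents. Whether it defines a wound baseline cannot be judged here.

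**It is late.** The SAP revision came after the N=90 assessment, with a new maximum of 105. A Day 0 repeat could then reach at most 105 − 90 = 15 subjects. This stands for the measurement, but not for the analysis changes, which cover everyone.

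**A stronger reading to avoid.** A reader might take the simulation curve in SAP 6.7 (event-free survival of 0.85, 0.70, 0.62 and 0.54 at 30, 60, 90 and 180 days) as the speed of pre-procedure change. It does not show that. It is an assumed curve for death or major amputation after enrolment, and it says nothing about wound area or class before the procedure.

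**Conclusion.** The point holds as a minor one. Protocol 5.2 and Table 1 allow the endpoint baseline for wound area and Rutherford class to be up to 180 days old, with no Day 0 repeat, and neither document tightens this for these measures. All Wound Area Reduction and Change in Rutherford Classification can therefore mix change before and after the procedure. The same old values can enter the exploratory models of SAP 9.6. The size and sign of the effect are unknown; they depend on the actual lags and on drift that the documents do not give.

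A reader might infer that the main result is compromised. It is not: the test of amputation-free survival against 0.54, its type I error, its power and the sample size do not depend on these baselines.

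Creatinine is a side point. Its baseline may be equally old, but the "Serum Creatinine" row of Table 1 has ticks only at baseline, 1 month and 6 months. With no value scheduled within 72 hours after the procedure, a fresh baseline alone would not make the nephropathy endpoint computable from scheduled data.

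**What to change.** 1. In Table 1, add a wound photograph with measurement and a Rutherford class to the Day 0 column, taken before the procedure, for subjects still to be treated.
2. In the SAP, define baseline for these measures as the last value before the procedure.
3. Report the distribution of the baseline-to-procedure lag for all subjects.
4. Repeat the wound-area and Rutherford analyses, and the SAP 9.6 models that use these variables, without subjects whose baseline is older than a limit that the sponsor pre-specifies. The documents give no basis for a particular cutoff, so the sponsor should choose and justify one before seeing the results.

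**Cost.** Step 1 is one photograph and one class assessment at an existing visit, a small site workload. Given how far enrolment had advanced, it may reach few subjects. Steps 2 to 4 need only assessment and procedure dates and apply to the whole cohort.
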